10.2 How might this information make specific individuals or families identifiable?

Since an indication for HBOC genetic counseling is common it is unlikely that individuals will be identifiable from this information.

10.3 If research data will be coded, how will access to the "key" for the code be limited? Include description of security measures (e.g., password-protected database, other). List names or positions of persons with access to the "key" for the code.

The client will generate the code word based off the prompt "first street you grew up on + first pets name." There will not be a key to link the code word with the clients. The code word is designed to be easy for clients to remember. If the study materials do not have consistent code words than the AI will attempt to match surveys based on one of the two prompted words. If this cannot be accomplished with reasonable certainty that documents are from the same client, then the data will not be included in analysis. Counselors will know the code word to attach it to the counselor post-visit survey but will not keep a record of the code word associated with identifying client information.

10.4 N/A

10.5 Will personally identifiable information be released to third parties?

The genetic counselors working with the project will know the code word label to record on their after-visit survey but will not keep a record of the code word associated with the patient name. No other third parties will have access to identifiable information.

10.6 Data sharing.

No data will be deposited in any repositories or databases. De-identified data could potentially be shared with other researchers in the future under an IRB approved amendment to this protocol or separate IRB-approved research protocol. Data shared would only include de-identified surveys, de-identified intervention, and demographic information.

10.7 Describe any additional features to protect confidentiality.

Gift cards will be sent to client participants who fill out the survey in person by having clients fill out an address card that is included in the survey information and returned separately. Online survey participants will enter gift card information through a separate link within the survey site.

Genetic counselors will be sent gift cards at the conclusion of the study by mail. Counselors will provide their addresses to the AI via email.

10.8 Loss or destruction of samples.

Any loss of data, either paper based surveys or breach of electronic data, will be reported promptly to the IRB.

## 11.0 Assessment of risk/benefit ratio

**Adults:** Research does not involve greater than minimal risk and involves the prospect of direct benefit to the individual subjects as well as yielding generalizable knowledge about improving genetic counseling practice. Efforts to reduce risk include those aimed at maintaining confidentiality and obtaining informed consent prior to survey completion.

**Pregnant women:** Research does not involve greater than minimal risk and involves the prospect of direct benefit to the individual subjects as well as yielding generalizable knowledge about improving genetic counseling practice. The research meets the criteria contained under 45 CFR 46.204 for research activities involving pregnant women.

## 12.0 Unanticipated Problems: Collection, monitoring, analysis and reporting of adverse events and protocol deviations

12.1 *N/A*

12.1.1 *N/A*

12.1.2 *N/A*

12.2 Describe plan to monitor and report adverse events and protocol deviations.

Protocol deviations, unanticipated problems, or non-compliance are defined as described in NIH HRPP SOP 16 ("Reporting Requirements for Unanticipated Problems, Adverse Events and Protocol Deviations"). All protocol deviations, unanticipated problems, or non-compliance occurring during the study, including those observed by or reported to the research team, will be recorded. Serious protocol deviations, unanticipated problems, or non-compliance will be reported to the IRB and CD (Clinical Director) as soon as possible but not more than 7 days after the PI first learns of the event. Not serious

protocol deviations, unanticipated problems, or non-compliance will be reported to the IRB and CD as soon as possible but not more than 14 days after the PI first learns of the event.

No adverse events, serious adverse events, or unanticipated adverse device effects are anticipated in this study since there are no medical devices or pharmaceutical interventions.

12.3 *N/A*

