## 1.0 Precipis

The proposed study is a feasibility study to assess the viability of implementing a Self-Affirmation (SA) intervention in a Hereditary Breast and Ovarian Cancer (HBOC) genetic counseling clinic to improve client communication and behavioral outcomes. Participants will be clients and genetic counselors at the St. Luke's Hospital System and Medstar Washington Hospital Center HBOC clinics. This study seeks to identify outcomes that would be most informative in a large-scale research protocol. As outcomes, we will assess clients' decision self-efficacy, intention to talk with family, genetic test uptake, empowerment, and HBOC knowledge. We will also assess counselors and clients perceived benefits, perceived harms, and acceptance of the affirmation intervention.

In this study clients will be invited to participate in an intervention before their genetic counseling appointment. The SA intervention is a short written exercise to reinforce clients' self-integrity (a global sense of personal adequacy), leading to more openness to threatening information within the genetic counseling session. Clients and counselors will be surveyed after the study to assess outcome measures and feasibility of the intervention.

Social science research has shown that when people are faced with threatening information they often seek to protect themselves and reject the threatening message. Message rejection can include minimizing the importance or discrediting the truth of the message. SA interventions aim to bolster self-integrity by focusing on aspects of subject's lives they value and thereby improving participants' self-perception and tolerance towards threatening messages. SA manipulations have been shown to increase patient communication within appointments and both intentions and actions toward behavior change.

Often in cancer genetic counseling appointments clients are confronted with the threat of having a significantly increased risk of cancers while being asked to make a decision about genetic testing. A self-affirmation intervention may facilitate greater client decision self-efficacy, empowerment, and positive behavior outcomes, such as communication with family regarding genetic risk and screening behaviors.

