Appendix C) (Creswell et al., 2013; Havranek et al., 2012). They will then be asked to write about the item that is most important to them and why it may be important to them. The control group will rank the same list and be asked to write about the 9th ranked item and why it might be important to someone else. The control condition is consistent with the control used in other SA intervention studies. The 9th ranked item is chosen to inhibit a reverse effect where participants feel affirmed because they do not value something that is aversive to them. Both the intervention and control group will receive a 6-question survey of state anxiety along with the writing prompt, which will be used as a control measure.

Potential participants will be identified through the patient schedule and will be contacted by the student assistant investigator (AI), [name], about one week prior to their appointment to invite them to participate in the study and obtain verbal informed consent. Participants will be recommended to arrive 15 minutes prior to their scheduled appointment. When clients arrive at the HBOC clinic, the front desk staff will give client participants the SA or control intervention based on random assignment. The affirmation intervention or control condition will be completed directly before the regularly scheduled appointment.

Genetic counselors will be blinded to the study condition of their clients, although clients might choose to discuss the content of the intervention survey with the counselor. Counseling sessions will otherwise proceed according to protocol for the clinic. Clients will receive a paper survey as they leave the appointment regarding their demographic information (age, sex, education, race, ethnicity, cancer status) experience in the study, decision self-efficacy, empowerment, genetic knowledge, intentions to talk with family, information seeking, and intentions to pursue genetic testing if it was offered. They will be given the option to fill out the paper version or to access an electronic version online. Hard copy surveys will be returned to the front desk or by mail to the AI. Electronic versions will be sent to an email address provided by the client. A week after their appointment, all clients will receive an electronic reminder notification to complete the questionnaire. Upon completion of the online survey or paper questionnaire participants will be mailed a \$15 gift card.

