Genetic counselors at St. Luke's Health System volunteered to participate in this study and contacted the AI about their interest in participating and hosting the study. The counselors at Medstar Washington Hospital Center were contacted by the AI after initial IRB approval of this protocol in order to increase recruitment by adding an additional site.

At the onset of data collection, counselors will complete a written consent. After each appointment with a study participant, genetic counselors will complete a short client empowerment survey. After the client study is complete, genetic counselors will be given a survey about their opinions about and experience with the self-affirmation intervention. Questions will include information on their experiences and opinions about the SA. Counselors at St. Luke's Health System will each be given a \$1400 gift card at the completion of the latter questionnaire. The counselors at Medstar see fewer potential participants so their compensation will be \$200. We expect to have approximately 16 patient participants from Medstar and 54 from St. Luke's Health System. In addition, the counselors at MedStar will be involved with recruitment over a shorter period of time and will not have to expend the effort expended by the St. Luke's counselors to work through logistics prior to the study's approval

**Figure 3:** *Participants participation in protocol*

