## **9.0 Description of likelihood and seriousness of harms and how safety will be maximized:**

This study is unlikely to cause serious harms. There is small chance that there could be low level psychological harm caused by this study because SA has been shown to increase openness to a threatening message and therefore increase feelings of vulnerability and possibly anxiety (Klein et al., 2011). While this may occur among participants in the intervention arm, the magnitude of the risk is likely small and will be mitigated by the fact that they will be seen by genetic counselors who have training to manage clients' anxiety. There also could be benefit to increasing anxiety in a situation where action needs to be taken to avoid a threat, such as continuing recommended screening for early detection of breast cancer. There is no increased risk to pregnant women or fetus related to this study protocol.

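### The psychological harm foreseen in section 9.0 has no clear recording category in 12.2, and counselor-perceived harms cannot be attributed to arm

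*Combined protocol and SAP*

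**What the plan says.** **Harm foreseen.** Section 9.0 says "There is small chance that there could be low level psychological harm caused by this study". The mechanism is that SA may "increase feelings of vulnerability and possibly anxiety". It places this in the intervention arm, judges the size of the risk to be small, and relies on the counselors' training in managing anxiety as mitigation. Section 9.5, which covers psychosocial harms, is marked N/A.

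**Recording.** Section 12.2 states "No adverse events, serious adverse events, or unanticipated adverse device effects are anticipated in this study" and gives the absence of devices and drugs as the reason. Its commitment is: "All protocol deviations, unanticipated problems, or non-compliance occurring during the study, including those observed by or reported to the research team, will be recorded". Serious items go to the IRB and Clinical Director within 7 days and others within 14. On definitions it says "Protocol deviations, unanticipated problems, or non-compliance are defined as described in NIH HRPP SOP 16". The title of that procedure mentions adverse events, but the procedure itself is not reproduced.

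**Counselor information.** Section 1.0 promises: "We will also assess counselors and clients perceived benefits, perceived harms, and acceptance of the affirmation intervention". Section 5.0 says "Genetic counselors will be blinded to the study condition of their clients", while allowing that a client may bring up the task. After each visit the counselor completes a counselor version of the GCOS-24, described in section 5.6 as a rating of client empowerment. On the intervention itself, section 5.0 says: "After the client study is complete, genetic counselors will be given a survey about their opinions about and experience with the self-affirmation intervention".

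**Client information.** Under section 5.6 the client survey asks whether the task affected the session and in what way. The six-item STAI is completed straight after the writing task and before the appointment. Section 7.0 uses it as a covariate.

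**The concern.** The one harm that the protocol names falls between its own categories. It is neither a deviation nor non-compliance. Because 9.0 foresees it, it is not naturally an unanticipated problem. Section 12.2 sets adverse events aside for a reason (no drug or device) that does not bear on a behavioural intervention. A client who becomes unusually anxious in session might or might not be recorded, depending on how a document outside the protocol is read.

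The counselor is the person whom 9.0 relies on to notice and manage anxiety. The described per-visit form does not ask about it. The counselor's view of the intervention is collected once, across sessions of both arms, without knowledge of arm.

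This is a feasibility study meant to inform a larger trial. If it reports that no adverse events occurred, a reader should be able to tell whether that reflects the clients or the recording rule.

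**Working it through.** The point rests on comparing sections. The plan gives no harm rate or harm-related figure to reproduce.

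**Step 1: does the foreseen harm fit a category in 12.2?**

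| Category | Does the 9.0 harm fit? |
|---|---|
| Protocol deviation | No: nothing in the protocol has been departed from |
| Non-compliance | No: same reason |
| Unanticipated problem | Unclear: 9.0 anticipates it, 12.2 does not; the definition lies in an outside procedure |
| Adverse event | Stated as not anticipated; not among the items to be recorded; no form or definition given |

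Sections 9.0, 9.5 and 12.2 disagree on whether the harm is expected, and the recording rule depends on the answer.

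**Step 2: which planned data bear on harm, and can they be linked to arm?**

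| Source | When | Linkable to arm? | Planned use |
|---|---|---|---|
| Client question on the task's effect on the session | After the visit; paper or online | Yes, by code word | Percent yes/no and themes (Aim 2); no comparison by arm stated |
| Short STAI | After the task, before the session | Yes, by code word | Covariate |
| Counselor GCOS-24 | After each visit | Yes, by code word (section 10.0) | Empowerment comparison and client-counselor correlation |
| Counselor end-of-study survey | Once, after the last client | No | Percent yes/no and themes (Aim 2) |

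The last row is the only described source of counselor-perceived harm. The appendices holding the forms are not in the documents, so this relies on the descriptions in section 5.6.

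**Step 3: how thin is the counselor source?** There are four counselors, so one answer moves a yes/no percentage by 100/4 = 25 points. Section 5.0 expects 54 clients at St. Luke's and 16 at Medstar, with two counselors at each. If clients divide evenly between counselors, which the documents do not say, each counselor looks back over 54/2 = 27 or 16/2 = 8 sessions, about half of them control. The planned number of after-visit forms is 54 + 16 = 70.

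**Step 4: what would per-visit recording give? (illustration only)** With 35 SA clients, all linked, and zero events, the one-sided 95% upper bound on the rate is 1 − 0.05^(1/35) = 8.2%. The chance of at least one event among 35 is 1 − (1 − p)^35. The documents give no rate, so p is an assumption over a range:

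| Assumed true rate p | Chance of at least one event |
|---|---|
| 2% | 51% |
| 5% | 83% |
| 10% | 97% |

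Thirty-five sessions could therefore be informative about a harm that is not very rare. They would not support a powered comparison between arms.

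**The case against.** **Harm data already exist.** A reader might infer that the trial collects nothing from which harm could be judged. The documents do not support that. The client survey asks about the task's effect on the session, section 1.0 promises clients' perceived harms as well as counselors', and the STAI measures anxiety, one of the effects named in 9.0, in both arms after the task. All can be linked to arm. What stands is narrower. None is tied to 12.2 or planned as a harm comparison. The STAI precedes the session, the client item depends on the survey being returned, and neither is the counselor's observation.

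**There is a reporting route.** A reader might also infer that nothing could reach the investigators during enrolment. That does not follow either. Section 12.2 covers events observed by or reported to the team and sets 7- and 14-day limits; section 5.0 has client surveys returned to the front desk or to the associate investigator; and no section says forms are held to the end. But the 12.2 route applies only if the event counts as one of its categories, and no planned step prompts a counselor to report.

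**The cited procedure may cover it.** This cannot be checked. One could also argue that, since 12.2 anticipates no such event, any that occurs is unanticipated and so recorded. That reading is possible, but it contradicts 9.0. The recording of the named harm should not depend on which section is read first.

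**The study is minimal risk.** This is so, and 9.0 adds that some rise in anxiety could be useful. It limits the weight of the point but does not remove the inconsistency.

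**A per-visit item could weaken blinding.** This stands if the item mentions the pre-visit task, because it could prompt discussion of the task just where the counselor rates empowerment. It determines how the item should be worded.

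**Conclusion.** The point holds as a modest, inexpensive improvement. Sections 9.0, 9.5 and 12.2 are inconsistent, and the recording rule does not clearly capture the low-level psychological harm that the protocol foresees. Counselor-perceived harms, promised in section 1.0, rest on four end-of-study opinions that cannot be attributed to arm, while about 70 arm-linkable counselor forms carry no described harm item.

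The conclusion assumes that the forms contain what section 5.6 describes, that the cited NIH procedure does not settle the category, and that counselors are not told the allocation before the final survey (the documents do not say). Even if they were told, that survey would still be a recollection over both arms. Linkage also assumes that code words match; section 10.3 leaves out records that cannot be matched. The 8.2% bound illustrates what systematic recording could offer and is not a property of the plan.

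**What to change.** 1. **Reconcile 9.0, 9.5 and 12.2.** List the psychological harm described in 9.0 as anticipated, state that it will be recorded, and remove the N/A at 9.5 or explain it.
2. **Add one item to the counselor after-visit form (Appendix E).** Use a yes/no question with free text on whether the client showed anxiety or upset beyond what is usual for such a session. Do not mention the pre-visit task, so that counselor blinding is protected.
3. **Add one descriptive table by arm.** Show the new item with exact confidence intervals, the client item on the task's effect on the session, and the post-task STAI. State that it is not a powered comparison.
4. **State that the forms are reviewed as they are received.** Keep the end-of-study counselor survey for opinions, barriers and facilitators.

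**Cost.** A few seconds on a form that already takes 3–5 minutes, one table, and revised wording in three sections. The item is subjective, since some anxiety is usual in cancer-risk counseling; blinded raters and comparison between randomised arms limit the harm this does.

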### **13.0 Description of alternatives to participation**

Participation in this study is completely voluntary for both clients and genetic counselors. There will be no negative consequences or changes in standard care for not participating or for withdrawing from the study.

### **14.0 Description of consent process**

14.1 Who will obtain consent (*PI, AIs*)?

A written informed consent review will be sent to all potential client participants along with the standard clinic information packet. The AI will call all potential participants a week prior to their appointment to consent clients, after they have received the information packet, and assess clients' interest in participating in the study.

Genetic counselors' consent will be obtained at the beginning of the study through a written consent document. Counselors will have an opportunity to ask the AI or PI questions regarding the consent through email or phone. Both the counselor and AI or PI will sign the informed consent and both parties will receive a copy by email.

14.2 Setting where consent will be obtained (*location of in-person discussion, phone, mail*).

Verbal consent will be obtained from clients by phone. An information leaflet describing the consent information will be included in the pre-appointment packet sent to all patients.

Written consent will be obtained from counselors in the medical office.

14.3 What information will be provided to participants? (*See attached consent appendix B.*)

On the initial phone call with potential client participants, the AI will explain the purpose of the study, the risks and benefits, the process of participation, the voluntary nature of the study, and withdraw information. The AI will explain that this is a study about using an intervention to improve the genetic counseling session.

The written consent document for counselors will explain the purpose of the study, the risks and benefits, the process of participation, the voluntary nature of the study, and withdrawal from the study.

- 14.4 Protections for participants who may be vulnerable to coercion or undue influences (*pregnant women, fetuses, children, people with impaired decision-making ability*).

Since this is a feasibility study to assess initial application of SA to a HBOC genetics clinic those with intellectual disabilities noted in their medical chart will not be referred by genetic counselors for study participation. Pregnant women will be included in the study population and we foresee no additional harms caused by study participation. Participants must be 18 years of age to participate.

This research involves no more than minimal risk.

- 14.5 Are there special circumstances regarding obtaining *consent*?

We are requesting a waiver of the requirement to obtain signed consent from client participants under the grounds of no more than minimal risk 45 CFR 46.110 (c). We believe this study meets the criteria for minimal risk and this waiver can be granted because “the research presents no more than minimal risk of harm to participants and involves no procedures for which written consent is normally required outside of the research context.” Counselor participants will complete a signed consent.

- 14.6 If this study involves collaborating sites, indicate if there is a single IRB review or if each site’s IRB will review their site’s participation in the study. Describe plans for ensuring appropriate IRB review and approval of consent forms at each site.

All client and genetic counselor participants will be from St. Luke’s Health System or Medstar Washington Hospital Center. The NIH will be the IRB of Record for St. Luke’s Health System. The reliance agreement forms have been submitted to the OHSRP. Concurrently to this amendment we are seeking exempt review through the Medstar Washington Hospital Center IRB.

